7.1.3 Reporting to Rigel Pharmaceuticals

7.1.3.1 Expedited Reporting Requirements for Serious Adverse Events

An investigator should report all SAEs as soon as possible after his/her awareness of the event via a MedWatch form to Rigel's authorized safety representative.

The MedWatch form should be sent to the following email or fax:

Email: [contact]
[contact]

The site may contact Rigel Drug Safety at the above fax/e-mail with questions regarding reporting of SAEs.

7.1.3.2 Pregnancy

Although pregnancy itself is not regarded as an AE, the initial notification and outcome of any pregnancy that occurs during the study must be documented. The pregnancy in a female study participant and the pregnancy outcome must be reported to Rigel Drug Safety within 24 hours of awareness. Partners that become pregnant by a male subject do not need to report pregnancy.

Prior to screening, females of childbearing potential must agree in the ICF to take appropriate measures to avoid pregnancy at all times during the study, commencing from the time of consent to 30 days after the last dose of study drug, and, if pregnancy occurs, they must agree to report the pregnancy and cooperate with the investigator as set forth below.

Should a pregnancy occur, the female study participant must immediately inform the investigator and must immediately discontinue study drug. The investigator should counsel the study participant on any risks of continuing the pregnancy and any possible effects on the fetus in view of the subject's participation in the study. The study participant must agree to follow-up by the investigator regarding the outcome of any pregnancy that occurs during the study. Outcome is defined as elective termination of the pregnancy, miscarriage, or delivery of the fetus. Any congenital anomaly/birth defect noted in the infant must be reported as an SAE.

7.1.4 Reporting to the FDA

The conduct of the study will comply with all FDA safety reporting requirements. **PLEASE NOTE THAT REPORTING REQUIREMENTS FOR THE FDA DIFFER FROM REPORTING REQUIREMENTS FOR HRPO/QASMC.** It is the responsibility of the Sponsor-Investigator to the FDA as follows:

- Report any unexpected fatal or life-threatening suspected adverse reaction (refer to Appendix D for definitions) no later than **7 calendar days** after initial receipt of the information.
- Report a suspected adverse reaction that is both serious and unexpected (SUSAR, refer to Appendix D) no later than **15 calendar days** after it is determined that the information qualifies for reporting. Report an adverse event (refer to Appendix D) as a suspected adverse reaction only if there is evidence to suggest a causal relationship between the drug and the adverse event, such as:
 - A single occurrence of an event that is uncommon and known to be strongly associated with drug exposure
 - One or more occurrences of an event that is not commonly associated with drug exposure but is otherwise uncommon in the population exposed to the drug

- An aggregate analysis of specific events observed in a clinical trial that indicates those events occur more frequently in the drug treatment group than in a concurrent or historical control group
- Report any findings from epidemiological studies, pooled analysis of multiple studies, or clinical studies that suggest a significant risk in humans exposed to the drug no later than **15 calendar days** after it is determined that the information qualifies for reporting.
- Report any findings from animal or in vitro testing that suggest significant risk in humans exposed to the drug no later than **15 calendar days** after it is determined that the information qualifies for reporting.
- Report any clinically important increase in the rate of a serious suspected adverse reaction of that listed in the protocol or IB within **15 calendar days** after it is determined that the information qualifies for reporting.

Submit each report as an IND safety report in a narrative format or on FDA Form 3500A or in an electronic format that FDA can process, review, and archive. Study teams must notify the Siteman Cancer Center Protocol Development team of each potentially reportable event within 1 business day after initial receipt of the information, and must bring the signed 1571 and FDA Form 3500A to the Siteman Cancer Center Protocol Development team no later than 1 business day prior to the due date for reporting to the FDA.

Each notification to FDA must bear prominent identification of its contents (“IND Safety Report”) and must be transmitted to the review division in the Center for Drug Evaluation and Research (CDER) or in the Center for Biologics Evaluation and Research (CBER) that has responsibility for review of the IND. Relevant follow-up information to an IND safety report must be submitted as soon as the information is available and must be identified as such (“Follow-up IND Safety Report”).

7.2 Exceptions to Expedited Reporting

Events that do not require expedited reporting as described in Section 8.1 include:

- planned hospitalizations
- hospitalizations < 24 hours
- respite care
- events related to disease progression

Events that do not require expedited reporting must still be captured in the EDC.

8.0 PHARMACEUTICAL INFORMATION

8.1 Fostamatinib

8.1.1 Fostamatinib Description

Fostamatinib is a tyrosine kinase inhibitor. Fostamatinib is formulated with the disodium hexahydrate salt of fostamatinib, a phosphate prodrug that converts to its pharmacologically active metabolite, R406, in vivo.

The chemical name for fostamatinib disodium hexahydrate is disodium (6-[[5-fluoro-2-(3,4,5-trimethoxyanilino) pyrimidin-4-yl]amino]-2,2-dimethyl-3-oxo-pyrido[3,2-b][1,4]oxazin-4-yl)methylphosphate hexahydrate. The molecular formula is $C_{23}H_{24}FN_6Na_2O_9P \cdot 6H_2O$, and the molecular weight is 732.52.

8.1.2 Clinical Pharmacology

Fostamatinib is a tyrosine kinase inhibitor with demonstrated activity against spleen tyrosine kinase (SYK). The major metabolite of fostamatinib, R406, inhibits signal transduction of Fc-activating receptors and B-cell receptor. The fostamatinib metabolite R406 reduces antibody-mediated destruction of platelets.

8.1.3 Pharmacokinetics and Drug Metabolism

Fostamatinib is a prodrug that is converted in the gut to the major active metabolite, R406. Mean (\pm standard deviation [SD]) exposure estimates of R406 are 550 (\pm 270) ng/mL for Cmax and 7080 (\pm 2670) ng \cdot h/mL for AUC. R406 exposure is approximately dose proportional up to 200 mg twice daily (1.3 times the 150 mg dosage). R406 accumulates approximately 2-to 3-fold upon twice daily dosing at 100–160 mg (0.67 to 1.06 times the 150 mg dosage). R406 is extensively metabolized, primarily through pathways of CYP450-mediated oxidation (by CYP3A4) and glucuronidation (by UDP glucuronosyltransferase [UGT]1A9). R406 is the predominant moiety in the systemic circulation, and there was minimal exposure to any R406 metabolites. Refer to the prescribing information of TAVALISSETM (fostamatinib) for details on drug-drug interaction potential.

8.1.4 Supplier

Fostamatinib will be supplied by Rigel Pharmaceuticals.

8.1.5 Dosage Form and Preparation

Fostamatinib is available as a 100 mg or 150 mg tablet.

8.1.6 Storage and Stability

Store at room temperature, 20°C to 25°C (68°F to 77°F); excursions permitted between 15°C to 30°C (59°F to 86°F). Do not remove desiccants.

8.1.7 Administration

Please refer to Section 6.3.

8.2 Ruxolitinib

8.2.1 Ruxolitinib Description

Ruxolitinib phosphate is a kinase inhibitor with the chemical name (R)-3-(4-(7H-pyrrolo[2,3d]pyrimidin-4-yl)-1H-pyrazol-1-yl)-3-cyclopentylpropanenitrile phosphate and a molecular weight of 404.36.

8.2.2 Clinical Pharmacology

Ruxolitinib, a kinase inhibitor, inhibits Janus Associated Kinases (JAKs) JAK1 and JAK2 which mediate the signaling of a number of cytokines and growth factors that are important for hematopoiesis and immune function. JAK signaling involves recruitment of STATs (signal transducers and activators of transcription) to cytokine receptors, activation and subsequent localization of STATs to the nucleus leading to modulation of gene expression.

MF and PV are myeloproliferative neoplasms (MPN) known to be associated with dysregulated JAK1 and JAK2 signaling. In a mouse model of JAK2V617F-positive MPN, oral administration of ruxolitinib prevented splenomegaly, preferentially decreased JAK2V617F mutant cells in the spleen and decreased circulating inflammatory cytokines (e.g., TNF- α , IL-6).

JAK-STAT signaling pathways play a role in regulating the development, proliferation, and activation of several immune cell types important for GVHD pathogenesis. In a mouse model of acute GVHD, oral administration of ruxolitinib was associated with decreased expression of inflammatory cytokines in colon homogenates and reduced immune-cell infiltration in the colon.

8.2.3 Pharmacokinetics and Drug Metabolism

Mean ruxolitinib maximal plasma concentration (C_{max}) and AUC increased proportionally over a single dose range of 5 mg to 200 mg. Mean ruxolitinib C_{max} ranged from 205 nM to 7100 nM and AUC ranged from 862 nM*hr to 30700 nM*hr over a single dose range of 5 mg to 200 mg.

Ruxolitinib is metabolized by CYP3A4 and to a lesser extent by CYP2C9. Refer to

the prescribing information of JAKAFI™ (ruxolitinib) for details on drug-drug interaction potential.

8.2.4 Supplier

Ruxolitinib is commercially available.

8.2.5 Dosage Form and Preparation

Ruxolitinib is available at 5 mg, 10 mg, 15 mg, 20 mg, and 25 mg tablets.

8.2.6 Storage and Stability

Store at room temperature 20°C to 25°C (68°F to 77°F); excursions permitted between 15°C and 30°C (59°F and 86°F)

8.2.7 Administration

Refer to Section 6.3.

9.0 DATA SUBMISSION SCHEDULE

Case report forms with appropriate source documentation will be completed according to the schedule listed in this section.

Case Report Form	Submission Schedule
Original Consent Form	Prior to registration
On-Study Form Medical History Form	Prior to starting treatment
CBC Form	Baseline, C1D1, C1D8, C1D15, C1D22, Weekly the first cycle of combination therapy and Day 1 & Day 15 of all other cycles
Treatment Form	Every cycle
Toxicity Form Transfusion Form	Continuous
Treatment Summary Form	Completion of treatment
Follow Up Form	Every 6 months for 2 years
Progression Form	Time of progression
Death Form	Time of death
Spleen Response Form	Baseline, end of Part A treatment, Cycle 4 Day 1, after 3 cycles in Part B, end of Part B treatment
MPN TSS Form	Day 1 of each cycle
MedWatch Form	See Section 8.0 for reporting requirements

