	
 3. Evaluate anemia response to fostamatinib 4. Evaluate the impact of fostamatinib on transfusion requirements 5. Evaluate the impact of fostamatinib on MF symptoms 6. Evaluate the ability of fostamatinib treatment to enable initiation with ruxolitinib 7. Evaluate the impact of fostamatinib on marrow fibrosis 
Part B:
 
Primary Objective: Evaluate the safety and tolerability of fostamatinib plus ruxolitinib in patients with MF and thrombocytopenia
 
Secondary Objectives:
 
 1. Evaluate spleen response with the combination of fostamatinib and ruxolitinib 2. Evaluate the impact of fostamatinib and ruxolitinib on symptoms 3. Evaluate the ability of fostamatinib to enable sustained treatment with ruxolitinib 4. Evaluate the impact of fostamatinib and ruxolitinib on marrow fibrosis
Endpoints:	
Part A:
 
Primary Endpoint: Platelet response as defined as an increase in platelet count $\geq 50K/\text{microL}$ with at least one more confirmatory platelet count separated by at least 2 weeks (in the absence of platelet transfusion) within the first 12 weeks of fostamatinib treatment
 
Secondary Endpoints:
 
 1. Platelet response by week 12 and at end of fostamatinib monotherapy treatment 2. Number of patients eligible to initiate therapy with ruxolitinib 3. Adverse events (AEs), serious AEs (SAEs), and laboratory abnormalities on fostamatinib treatment 4. Patients who permanently discontinued fostamatinib due to fostamatinib related AEs 5. Patients who required treatment interruption of fostamatinib due to AEs 6. Patients who were dose escalated who tolerated fostamatinib dose greater than 100 mg BID 7. Patients who achieve 35% or greater reduction in spleen volume as determined by ultrasound at week 12 of fostamatinib treatment and end of fostamatinib monotherapy treatment

	
 8. Mean reduction in spleen volume as determined by ultrasound at week 12 of fostamatinib treatment and end of fostamatinib monotherapy treatment 9. Patients with 50% or greater improvement in Total Symptom Score at week 12 of treatment and end of fostamatinib monotherapy treatment 10. Patients who achieve platelet transfusion independence 11. Patients with anemia who achieve RBC transfusion independence 12. Change in marrow fibrosis by WHO grading

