	
Part B:
 
Primary Endpoint: Incidence, severity, and outcomes of AEs per NCI CTCAE v 5.0, SAEs, AEs of interest (AEIs) and laboratory abnormalities during fostamatinib and ruxolitinib treatment

	
Secondary Endpoints:
 
 1. Patients with 35% or greater reduction in spleen volume as determined by ultrasound after 12 weeks of combination therapy and end of treatment 2. Mean reduction in spleen volume as determined by ultrasound after 12 weeks of combination therapy and end of treatment 3. Patients with a 50% or greater improvement in Total Symptom Score after 12 weeks of combination therapy and at end of treatment 4. Duration of uninterrupted ruxolitinib treatment 5. Change in marrow fibrosis by WHO grading
Study Population:	Twelve adult patients of any race or ethnicity with primary or secondary myelofibrosis with severe thrombocytopenia (platelet count < 50K/microL) with intermediate or high risk disease by IPSS.
Phase:	Pilot Phase II Study
Description of Sites / Facilities Enrolling:	This study will be active at Washington University School of Medicine.
Description of Study Intervention:	Both fostamatinib and ruxolitinib are oral drugs taken twice daily on a continuous basis.
Study Duration:	2 years
Participant Duration:	48 weeks

STUDY SCHEMA

[figure not shown]
Part A:

The starting dose of fostamatinib is 100 mg twice daily (BID). After the first cycle, if no major dose related safety issue is observed and the platelet count is less than 50K/microL, then the fostamatinib dose will be increased to 150 mg BID for the next 2 cycles; otherwise the dose may be continued at 100 mg BID.

Part B:

After 3 cycles of fostamatinib monotherapy, all patients with a sustained platelet count \geq 50K/microL, will continue on the current fostamatinib dose plus ruxolitinib at the recommended dose per standard prescribing guidelines for an additional 9 cycles.

Patients who do not reach platelet count of at least 50K/microL but who achieve clinical benefit per the treating provider may continue on single agent fostamatinib for up to 12 total treatment cycles. If these patients achieve a sustained platelet count of \geq 50K/microL at any point prior to Cycle 10 Day 1, then they may be eligible to enroll in Part B of the study and continue treatment with fostamatinib and ruxolitinib for the remainder of the study.

SCHEDULE OF ACTIVITIES

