	Screening ¹	D1 of each cycle ²	D15 of each cycle	EOT Part A	C4D1	After 3 cycles Part B	EOT Part B	Follow-up ³
Informed consent	X							
H&P, ECOG PS, con med	X	X						
Medical history	X							
CBC	X	X ⁴	X ⁴					
Select chemistry ⁵	X	X	X					
PT/INR, PTT	X							
Lipid Panel ⁶	X	X ⁶						
Pregnancy test ⁷	X	X						
ECG	X							
Abdominal ultrasound for spleen volume ⁸	X			X	X	X	X	
Bone marrow biopsy	X ⁹			X ⁸			X ⁸	
MPN symptom assessment form		X						
Fostamatinib		Oral drug taken on a twice daily basis						
Ruxolitinib		As per SOC						
AE assessment		Start of treatment through 30 days after last day of study treatment						
Progression and survival								X

1. Screening evaluations must be conducted within 3 weeks prior to the start of therapy.
2. Each cycle is 28 days. +/- 3 day for Day 1 assessments
3. Every 6 months for up to 2 years.
4. Also on D8 and D22 (weekly) the first cycle of fostamatinib monotherapy and first cycle of fostamatinib + ruxolitinib combination therapy (+/- 2 days)
5. BUN, creatinine, total bilirubin, AST, ALT, albumin
6. Total Cholesterol, LDL, HDL, non-HDL, Triglycerides, check every 2 cycles after starting ruxolitinib therapy
7. Women of childbearing potential only; test may be a urine test, and if positive, confirm with a serum test.
8. +/- 7 days
9. May be done up to 30 months before signing consent

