2.0 OBJECTIVES AND ENDPOINTS

2.1 Part A Objectives and Endpoints

Objectives	Endpoints	Justification for Endpoints
Primary		
To evaluate the impact of fostamatinib on platelet counts in patients with myelofibrosis and severe thrombocytopenia	Platelet response as detailed in Section 11.2.2, platelet response by week 12 and end of fostamatinib monotherapy treatment, and number of patients eligible to initiate treatment with a JAK2 inhibitor (ruxolitinib)	The efficacy of fostamatinib on thrombocytopenia in MF patients is unknown
Secondary		
To evaluate the safety and tolerability of single agent fostamatinib in patients with MF and thrombocytopenia	Incidence, severity, frequency, and outcomes of AEs and SAEs as defined by CTCAE v5.0 criteria, AEIs, laboratory abnormalities, and number of patients who permanently discontinue fostamatinib due to fostamatinib-related AEs, number of patients who require treatment interruptions due to fostamatinib-related AEs	The safety and tolerability of fostamatinib in MF patients is unknown.
To evaluate spleen response in patients with MF receiving fostamatinib	Spleen response as detailed in Section 11.4 at week 12 and end of fostamatinib monotherapy treatment, mean reduction in spleen volume as determined by ultrasound at week 12 and end of fostamatinib monotherapy treatment	The efficacy of fostamatinib on reducing spleen size in MF patients is unknown
To evaluate anemia response in patients with MF receiving fostamatinib	Anemia response as detailed in Section 11.2.1	The impact of fostamatinib on anemia in MF patients is unknown

To evaluate the impact of fostamatinib on constitutional symptoms in patients with MF	Constitutional symptoms as detailed in Section 11.3 at week 12 and end of fostamatinib monotherapy treatment	The efficacy of fostamatinib on improving symptoms in MF patients is unknown
To evaluate the impact of fostamatinib on transfusion requirements	Number of patients who achieve platelet and RBC transfusion independence who were previously requiring transfusions	The impact of fostamatinib on transfusion burden in MF patients is unknown
To evaluate the impact of fostamatinib on marrow fibrosis	Change in marrow fibrosis per WHO grading on bone marrow biopsy performed at the end of fostamatinib monotherapy	The impact of fostamatinib on marrow fibrosis is unknown

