2.2 Part B Objectives and Endpoints

Objectives	Endpoints	Justification for Endpoints
Primary		
To evaluate the safety and tolerability of the combination of fostamatinib and ruxolitinib in MF patients	Incidence, severity, frequency, and outcomes of AEs and SAEs as defined by CTCAE v5.0 criteria and AEs of interest (AEIs) as defined in section 5.5	The safety of this combination therapy in MF patients is not known.
Secondary		
To evaluate the spleen response in patients with MF receiving fostamatinib in combination with ruxolitinib	Spleen response as detailed in Section 11.4 after 12 weeks of combination therapy, mean reduction in spleen volume as determined by ultrasound after 12 weeks of combination therapy and at the end of treatment	The efficacy of fostamatinib in combination with a JAK inhibitor on reducing spleen size in patients with MF is unknown
To evaluate the impact of fostamatinib in combination with ruxolitinib on constitutional symptoms in patients with MF	Constitutional symptoms as detailed in Section 11.3 after 12 weeks of combination therapy and at the end of treatment	The efficacy of fostamatinib in combination with a JAK inhibitor on symptoms in MF is unknown
Evaluate the ability of fostamatinib to enable sustained treatment with ruxolitinib	Duration of uninterrupted JAK inhibitor (ruxolitinib) therapy	The ability of fostamatinib to maintain an adequate platelet count for patients

		to remain on JAK inhibitor therapy is unknown
To evaluate the impact of fostamatinib and ruxolitinib on marrow fibrosis	Change in marrow fibrosis per WHO grading on bone marrow biopsy performed at the end of fostamatinib and ruxolitinib therapy	The impact of fostamatinib and ruxolitinib combination therapy on marrow fibrosis is unknown

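### Symptom response is an endpoint at the end of monotherapy and at the end of treatment, but the symptom form is scheduled only at cycle Day 1 visits

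*Combined protocol and SAP*

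**What the plan says.** **Endpoints.** The Synopsis lists, for Part A, "Patients with 50% or greater improvement in Total Symptom Score at week 12 of treatment and end of fostamatinib monotherapy treatment", and for Part B, "Patients with a 50% or greater improvement in Total Symptom Score after 12 weeks of combination therapy and at end of treatment". Sections 2.1 and 2.2 repeat the time points: "Constitutional symptoms as detailed in Section 11.3 at week 12 and end of fostamatinib monotherapy treatment" and "Constitutional symptoms as detailed in Section 11.3 after 12 weeks of combination therapy and at the end of treatment". The response definition itself is in Section 10.3, so the section number in that cross-reference is out of date. The time points agree throughout.

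**Collection.** In the Schedule of Activities the row "MPN symptom assessment form" has one mark, in the column for cycle Day 1 visits. The table has separate columns for the end of Part A and the end of Part B. Ultrasound and marrow biopsy are marked in both; the symptom form is in neither. Section 9.0 gives the same timing for the MPN TSS Form: "Day 1 of each cycle". The Spleen Response Form, one row above it, is due at "Baseline, end of Part A treatment, Cycle 4 Day 1, after 3 cycles in Part B, end of Part B treatment".

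**Timing and follow-up.** Footnote 2 to the Schedule of Activities reads "Each cycle is 28 days. +/- 3 day for Day 1 assessments". Total treatment runs to 48 weeks (Section 5.3). Section 5.10 sends patients who stop early to the study calendar, whose follow-up column contains only progression and survival.

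**Analysis.** Section 12.3 promises the symptom response rate and the overall response rate with exact 95% confidence intervals. It does not say which form supplies the end-of-treatment value.

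**The concern.** An endpoint is defined at two time points for which the plan schedules no measurement. The spleen endpoint shares those time points and does have its assessments, so the symptom row looks like an omission and not a deliberate choice.

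If sites follow the schedule exactly, the analyst will have to decide after the data are in whether a patient without an end-of-treatment form is missing or is represented by the last Day 1 form. The two choices need not agree. For a patient who stops mid-cycle because of toxicity or progression, the last Day 1 form may predate the event that ended treatment. A score that was never collected cannot be recovered later.

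The effect can go one step beyond the symptom rate. Under Section 10.1, a symptom response can by itself qualify a patient for clinical improvement, provided there is no progression or worsening of cytopenias. Clinical improvement counts towards objective response. An undefined symptom result can therefore leave overall response undefined for a patient whose only response is in symptoms.

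**Working it through.** The plan states no figure to reproduce here. The check sets the visit calendar against the endpoint time points.

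**Inputs**
- Cycle length of 28 days and a Day 1 window of 3 days either side: Schedule of Activities, footnote 2.
- Maximum treatment of 48 weeks, which is 12 cycles: Section 5.3.
- Symptom form at cycle Day 1 visits only: Schedule of Activities and Section 9.0.

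**Step 1: when forms are due.** Day 1 of cycle c falls at week 4 × (c − 1). For cycles 1 to 12 this gives weeks 0, 4, 8, 12, and so on up to 44. Cycle 12 ends at 12 × 4 = week 48, and no Day 1 visit follows it.

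**Step 2: a patient who completes 12 cycles.** The last form is at week 4 × (12 − 1) = 44. The gap to the end of treatment is 48 − 44 = 4 weeks, or 28 days. With the Day 1 window it is 28 − 3 = 25 to 28 + 3 = 31 days before the nominal end. This applies equally to a patient who finishes in Part B and to one who stays on monotherapy for all 12 cycles.

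**Step 3: a patient who stops mid-cycle.** If treatment stops on day d of a cycle, the last scheduled form is nominally d − 1 days old. A stop on day 15, for example, gives 15 − 1 = 14 days. No form is due at the stop, and the follow-up column adds none.

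**Step 4: each endpoint time point against the schedule**

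| Time point | Symptom form due? |
|---|---|
| Baseline | Yes: cycle 1 Day 1, week 0 |
| Week 12 | Yes: cycle 4 Day 1, 4 × 3 = week 12 |
| 12 weeks of combination | Yes: Day 1 of the fourth combination cycle, where there is one |
| End of monotherapy, patient enters Part B on a Day 1 | Yes: that visit's form |
| End of monotherapy, patient leaves at the cycle 4 Day 1 visit | Yes: that visit's form |
| End of monotherapy, patient stops mid-cycle or completes 12 cycles | No |
| End of treatment, Part B | No, unless treatment happens to end at a Day 1 visit |

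There is one boundary case in the third row. A patient whose combination therapy starts only at cycle 10 Day 1 (week 36) reaches 12 weeks of it at 36 + 12 = week 48. That is the same point as the end of treatment, so the same added form would serve.

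**Step 5: comparison with spleen assessment.** Ultrasound is marked at the end of Part A and the end of Part B, and Section 9.0 has a spleen form at both. The two tables agree with each other on both instruments, so a lost table cell is an unlikely explanation for the missing symptom form.

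**The case against.** The strongest reply is that forms are collected every 28 days, so the last Day 1 form can stand in. A completer has a week-44 score, the fixed 12-week time points are generally covered, and every analysis is descriptive in a hypothesis-generating pilot. That stands as a limit on size. It does not close the gap, because nothing in the plan says that the last Day 1 form is the end-of-treatment value.

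Three stronger readings may tempt a reader, and the documents do not support them.

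- **That nearly every patient lacks an end-of-monotherapy score.** Patients who enter Part B on a Day 1, or who leave at the cycle 4 Day 1 visit, have one. The number affected cannot be taken from the 20% and 40% response rates in Section 12.4. Those illustrate the platelet-response calculation and are not rates of entry to Part B, which stays open until cycle 10 Day 1.
- **That a mid-cycle ruxolitinib start leaves entry to combination therapy without a form.** Section 5.3 allows an earlier start at the investigator's discretion but does not describe a mid-cycle one. The schedule counts combination therapy in its own cycles, with weekly blood counts in the first, which implies a Day 1 at entry.
- **That the total score is wrongly built because fatigue is left out.** Appendix F collects fatigue as an unnumbered item and tells the site to sum questions 1 to 9. Section 10.3 refers to that form. The rule is explicit and the two places agree. A suspicion that fatigue belongs in the total would rest on a source outside these documents.

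**Conclusion.** The point holds as a mismatch between endpoint and schedule. Followed as written, the plan collects no symptom form at the end of treatment for a patient who completes 12 cycles (last form nominally 28 days early, 25 to 31 with the visit window) or for one who stops mid-cycle. It also gives no rule for filling the gap.

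The figures assume 28-day cycles without delay and treatment ending at week 48. The number of patients affected, and the resulting shift in the response rate, cannot be computed: the documents do not say how many will enter Part B, stop mid-cycle or complete 12 cycles.

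The consequence is limited to secondary descriptive endpoints, plus overall response where it rests on symptom response alone. A reader might infer that the trial's main conclusions are at risk. They are not: platelet response, the Part B safety endpoint and the stopping rule do not use the symptom form. The change should be made because it is cheap and the missing scores cannot be collected afterwards.

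**What to change.** 1. In the Schedule of Activities, mark the symptom form in the end-of-Part-A and end-of-Part-B columns.
2. In Section 9.0, add the same two time points to the MPN TSS Form row, in line with the spleen form.
3. In Section 10.3 or 12.3, state before the data are analysed how a patient with no end-of-treatment form is handled. One option is to use the last Day 1 form and report the interval from that form to the end of treatment; another is to treat the patient as missing at that time point.
4. Where a patient enters Part B or leaves at a Day 1 visit, say that the form from that visit serves as the end-of-monotherapy score, so that it is not collected twice.

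The cost is two schedule cells, one table row and a sentence or two of text. Patients complete one more one-page questionnaire at time points that already include an ultrasound. Sample size, visits and the primary analyses do not change.
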